5.3.8 Trial partners

Patients will be asked to nominate a Trial Partner that the clinical research team can contact if the patient cannot respond during the trial period e.g. if the patient is sick at home, or because they are in hospital or have died. This is not a requirement of trial participation but a proposed way of supporting the patient's participation on the trial.

5.3.9 Expenses and benefits

Reasonable travel expenses for any visits additional to normal care will be reimbursed, although no such additional visits are envisaged to be required.

6 PATIENT SELECTION

During the trial, there will be ongoing review of the emerging data to inform adaptive decision making if required. Patient enrichment strategies may be implemented e.g. revision to inclusion criteria regarding co-morbidities, neutrophil/lymphocyte ratios, age.

6.1 Inclusion Criteria

1. Patient willing and able to give informed consent.
2. Adults, 18 years of age and above
3. Symptomatic COVID-19 infection
4. Evidence of current COVID-19 infection from a validated assay.

6.2 Exclusion Criteria

The patient may not enter the trial if ANY of the following apply:

1. Significant electrolyte disturbance (e.g. hyperkalaemia, potassium > site specific upper limit of normal).
2. Alanine aminotransferase (ALT) and/or aspartate aminotransferase (AST) and/or alkaline phosphatase (ALP) $\geq 2.5 \times$ ULN.
3. Any condition that, in the Investigator's opinion, would not make the patient a good candidate for the clinical trial or would prevent adequate compliance with trial therapy e.g. mild cognitive impairment (unable to follow instructions for self-assessment readings as assessed by the Investigator).
4. Patients on long term supplementary oxygen requirement (patients for whom hospital admission would not be considered e.g. care plan in the community is in place, are not excluded).
5. Known hypersensitivity to camostat.
6. Platelet count $<100 \times 10^9/L$.
7. Co-enrolment with a Clinical Trial of an Investigational Medicinal Product (CTIMP) will not be permitted. Co-enrolment with a clinical investigation of a Medical Device or a non-interventional clinical study will be considered on a study-by-study basis and in discussion with the relevant Chief Investigators and Sponsors and industrial collaborators.
8. Co-enrolment involving non-interventional research (including questionnaire or tissue only studies) will be allowed provided this is not expected to affect the outcomes of both studies or place undue burden upon participants and their families.
9. Female patients who are able to become pregnant⁷ (or are already pregnant or lactating). However, those patients who are of child bearing potential and have a negative serum or urine pregnancy test before enrolment and agree to use two forms of contraception (one effective form plus a barrier method [oral, injected or implanted hormonal contraception

⁷ A woman is considered of childbearing potential i.e. fertile, following menarche and until becoming post-menopausal unless permanently sterile. Permanent sterilisation methods include hysterectomy, bilateral salpingectomy and bilateral oophorectomy. Post-menopausal state is defined as no menses for 12 months without an alternative medical cause. A high follicle stimulating hormone (FSH) level in the postmenopausal range may be used to confirm a post-menopausal state in women not using hormonal contraception or hormonal replacement therapy. However, in the absence of 12 months of amenorrhea, a single FSH measurement is insufficient.

and condom; intra-uterine device and condom; diaphragm with spermicidal gel and condom]) or agree to sexual abstinence^{*8}, effective from the first administration of camostat, throughout the trial and for 28 days afterwards are considered eligible.

(*Abstinence is only considered to be an acceptable method of contraception when this is in line with the preferred and usual lifestyle of the subject. Periodic abstinence (e.g. calendar, ovulation, symptothermal, post-ovulation methods) and withdrawal are not acceptable methods of contraception.)

10. Male patients with partners of child-bearing potential⁷(unless they agree to take measures not to father children by using a barrier method of contraception [condom plus spermicide] or to sexual abstinence^{*8} effective from the first administration of camostat, throughout the trial and for 28 days afterwards. Men with partners of child-bearing potential must also be willing to ensure that their partner uses an effective method of contraception for the same duration for example, hormonal contraception, intrauterine device, diaphragm with spermicidal gel or sexual abstinence). Men with pregnant or lactating partners must be advised to use barrier method contraception (for example, condom plus spermicidal gel) to prevent exposure of the foetus or neonate.

(*Abstinence is only considered to be an acceptable method of contraception when this is in line with the preferred and usual lifestyle of the subject. Periodic abstinence (e.g., calendar, ovulation, symptothermal, post-ovulation methods) and withdrawal are not acceptable methods of contraception.).

11. Significant cardiovascular disease (as assessed via the participant's medical record and history) as defined by:
 - a. History of congestive heart failure requiring therapy (New York Heart Association [NYHA] III or IV – Appendix 3).
 - b. History of unstable angina pectoris or myocardial infarction up to 6 months prior to trial entry.
 - c. Presence of severe valvular heart disease.
 - d. Presence of a ventricular arrhythmia requiring treatment.

Known allergic reactions to components of camostat e.g., lactose intolerance (see Section 7.2.1)

7 PHARMACEUTICAL INFORMATION

Please see IB supplement and SmPC for further information if required.

7.1 Supply of Investigational Medicinal Product

A complete Certificate of Analysis (CoA) and a Qualified Person (QP) certification must be provided with each delivery of camostat.

For information on camostat and re-ordering of supplies, contact the Clinical Research Associate (CRA)/Clinical Study Manager (CSM) responsible for the trial who will arrange further supplies.

Camostat will be supplied by:

Fisher Clinical Services U.K. Limited

⁸ *Abstinence is only considered to be an acceptable method of contraception when this is in line with the preferred and usual lifestyle of the subject. Periodic abstinence (e.g., calendar, ovulation, symptothermal, post-ovulation methods) and withdrawal are not acceptable methods of contraception.*

The Manufacturing Organisation (Fisher Clinical Services U.K. Limited) must provide confirmation of the shipment to the CSM/CRA on despatch of the investigational medicinal product (IMP).

The primary and secondary packaging for the IMP will be labelled according to Eudralex Volume 4: Annex 13 'Manufacture of Investigational Medicinal Products' of the European Union guide to Good Manufacturing Practice (GMP).

Upon arrival at site, patient ID must be added to the applicable variable fields on the primary and secondary labels.

An example of the approved label can be found in the Trial Master File (TMF).

7.2 Pharmaceutical Data

7.2.1 Formulation of camostat

Camostat (camostat mesilate marketed as [FOIPAN®]) will be supplied as 100mg tablets.

Other ingredients as follows: Hydroxypropylcellulose, Carmellose calcium, Magnesium Stearate, Polyoxyethylene (105), polyoxypropylene (5) glycol, Lactose hydrate.

7.2.2 Storage conditions

All supplies must be stored in a secure, limited access storage area in its original packaging. Camostat must be stored at room temperature.

7.2.3 Stability and labelling of camostat

The tablets are supplied in boxes containing 5 blister packs. Patients should be instructed to store camostat at room temperature and out of sight and reach of children.

Labelling applied by pharmacy for camostat must include the following information:

Name of IMP; dose; expiry time/date; patient ID (and any other local requirements e.g. Pharmacy batch number).

NB: Any Pharmacy applied labels must not obscure the Annex 13 labels applied by the Manufacturing Organisation. Example labels should be filed in the TMF and approved by the Sponsor.

7.2.4 Dispensing of camostat

Sufficient tablets of camostat must be dispensed on each occasion to cover the prescribed dose for the full treatment period i.e. Days 1-14.

Patients should be supplied with the required quantity of camostat in the original boxes to cover the prescribed dose. Blister packs must not be cut to reduce tablet numbers at dispensing.

The tablets are supplied in blister packs and must not be removed from the primary packaging (provided to the patient) and placed in any other container. Tablets should be stored at room temperature and out of sight and reach of children.

7.2.5 Camostat administration

For patients randomised to the treatment arms:

Before dispensing the camostat tablets, the exact dosage must always be double-checked by a second suitably qualified person. All checks and double-checks must be documented (signed and dated) and the documentation must be available for the CRA/CSM to verify.

The camostat tablets must be swallowed whole (with water) and not chewed, crushed, dissolved or divided. Patients will be provided with instructions for when they should take their camostat.

Patients will be asked to take their camostat four times a day, one hour before each meal. After the patient has finished eating, they should wait approximately three hours before taking the next dose. Again, the patient should wait one hour after dosing before they can eat. The patient should aim to take their last dose of camostat before they go to bed.

Patients should be advised that there should be approximately a four-hour interval between doses, except between their last dose of the day and the next dose the following morning; this overnight interval will be longer.

Should a patient miss a scheduled dose in error, for example, forgetting to take the dose, then the patient can take that delayed dose within two hours of the scheduled dose (but will need to refrain from eating for an hour afterwards). Subsequent doses will be delayed accordingly.

The patient will be supplied with a diary card and asked to record each dose (time and dose) and timing of each meal.

For dose modification guidance, see Section 5.3.2.

7.2.6 Camostat accountability

Accurate records of all IMP shipments, tablets dispensed, and all IMP returned must be maintained. This inventory record must be available for inspection at any time by clinical research associates (CRAs) or CSMs of the Sponsor. Investigational Medicinal Product supplies are to be used only in accordance with this protocol and under the supervision of the Investigator.

The Investigator undertakes not to destroy any unused or returned IMP unless authorised to do so by the Sponsor. Any unused IMP must be destroyed according to hospital procedures and properly accounted for using the IMP Destruction Form and on the IMP Accountability Record. During the course of the trial the CRA will check the numbers of camostat tablets shipped to the centre, the number used, and the number destroyed or returned. The pharmacy will give an account of any discrepancy.

7.2.7 Camostat supply to primary and secondary care pharmacies

For trial sites affiliated to a hospital Trust/Board, camostat will be supplied to the hospital pharmacy and maintained by the clinical trial pharmacists.

If trial sites are opened where camostat is to be held in secondary pharmacies e.g. GP pharmacies, the Sponsor will perform a risk assessment to confirm the process by which camostat is managed and dispensed to patients and document this in the risk assessment and site management plan.

8 TRIAL PROCEDURES

8.1 Baseline assessments

All patients must have received a positive COVID-19 test result via oropharyngeal/nasopharyngeal swab (or other validated method) prior to baseline assessments being performed. [REDACTED]

[REDACTED] Other validated methodology may be used during the course of the trial e.g. saliva test, to improve the patient experience and assuming equal to or improved test validation and sensitivity.

When the patient has indicated their interest in the trial as per Section 6, the following information will be ascertained by the clinical research team member via an initial conversation (via video or phone call for community patients)*:

- Demographics – date of birth, gender.
- Height and weight.

CONFIDENTIAL

- Symptoms of COVID-19, ancillary symptoms and length of symptoms – e.g. fever ($\geq 37.8^{\circ}\text{C}$), persistent dry cough, muscle pain, shortness of breath, diarrhoea, headache, anosmia, other symptoms.
- COVID-age risk (Appendix 4)
- Other potential risk factors including smoking (pack year history), ethnicity, occupation, symptomatic household (or other) contact, other relevant medication history.
- Previous medical history – particularly chronic disease (specifically hypertension, cardiovascular disease, diabetes mellitus, hyperlipidaemia, cancer and existing respiratory conditions), history of influenza vaccination and COVID-19 vaccination (past two years).

*Alternatively, for patients recruited in a hospital setting, all baseline assessments would be performed during their attendance in the hospital, including a COVID-19 test if not previously performed.

If the above assessments are supportive of a home visit to conclude the below eligibility assessments, the patient will be asked to provide consent as per Section 9.2. The following will then be performed:

- Biochemical and haematological investigations to include:
 - Haematology – haemoglobin (Hb), white blood cells (WBC), neutrophils, lymphocytes, and platelets.
 - Biochemistry – sodium, potassium, magnesium, adjusted calcium, phosphate, urea, creatinine, total protein, albumin, bilirubin, alkaline phosphatase (ALP), alanine aminotransferase (ALT), aspartate aminotransferase (AST), clotting- prothrombin time (PT), activated partial thromboplastin time (APTT), gamma-glutamyl transferase (GGT), troponin, D-dimer.

Radiological investigations over normal clinical care are not required as part of this trial, but if performed as part of clinical care, chest x-rays and chest CT scans will be assessed and included in analysis by accessing the secondary care patient records.

Additional laboratory investigations or procedures performed as part of clinical care during the trial period will be included in the analysis.

8.2 Confirmation of eligibility

Patients with a positive COVID-19 result and who are eligible according to the inclusion/exclusion criteria (post review of the assessments performed during baseline assessments), will be contacted by the clinical research team. They will be randomised by the clinical research team and informed of their allocated group.

8.3 On study assessments/procedures

All patients will be contacted as follows:

8.3.1 Days 1-14: Daily monitoring via video or phone call

Community patients will be monitored via video or phone call daily. If feasible for hospital patients daily monitoring will be performed face to face.

- [REDACTED]
- [REDACTED]
- [REDACTED]
- [REDACTED]

Number of patients asked to perform this test and days of testing may be adapted based on test availability.

- [REDACTED]
- Ordinal scale status assessment (as per secondary endpoint).

Those patients who have consented can enter their data

[REDACTED] on the Medidata patient application 'app'.

The video (phone) calls made to the patient may be recorded for quality assurance purposes. Patients will be asked to consent to recording of their calls during the main consenting process and at the beginning of each call, the patient will be asked to verbally confirm their consent. These recordings will be emailed immediately afterwards to a secure NHS email address where they will be stored securely on the NHS server until the end of the trial. See Section 14.3.1. This is not a requirement of trial participation but a proposed way of supporting the patient's participation on the trial.

8.3.2 Days 7 and 14: Home visit consultation with clinical professional

The intention is that for community patients **home visits** occur on Days 7 and 14 to take research bloods [REDACTED]. However, this requirement may change if patients are able to provide samples by visiting the site but only in accordance with government and clinical advice. For those patients in hospital, Day 7 and 14 visits can occur in hospital face to face. If the Sponsor and site decide that sampling is not required, this will be communicated to the patient. The Days 7 and 14 video (phone) calls will still go ahead as planned regardless of sampling.

- [REDACTED]
- Biochemical and haematological investigations to include:
 - Haematology – Hb, WBC, neutrophils, lymphocytes, and platelets.
 - Biochemistry – sodium, potassium, magnesium, adjusted calcium, phosphate, urea, creatinine, total protein, albumin, bilirubin, ALP, ALT, AST, clotting-PT, APTT, GGT, troponin, D-dimer.

- Raised parameters will be managed as per usual Trust clinical management. If results indicate that the patient should be admitted, the clinical research team will contact the patient and arrange for them to come into hospital for further assessment. For dose interruption/withdrawal criteria, see Section 5.3.3

- [REDACTED]
- Blood sample for pharmacokinetics (PK) assessment (patient will be asked to consent to PK sampling within main study ICD and that this will also be document within the patient's medical notes)

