A clinical research team member will call the patient daily during this period. On Days 7 and 14, patients will be visited at home by the clinical research team, for blood draws and COVID-19 swab (or equivalent) testing. Home visits may be replaced by patient site visits (e.g. to a 'red hub') but only in accordance with government and clinical advice. If the Sponsor and site decide that sampling is not required, this will be communicated to the patient. The video (phone) calls on Days 7 and 14 will still go ahead as planned regardless of sampling. Patients will also be called weekly (Days 21 and 28) before the follow up period ends.

Patients who are in hospital for non COVID-19 related reasons may be recruited if they tested positive while in hospital. In this situation daily phone calls may be substituted by face to face visits, if feasible, by the hospital team until the patient is discharged. At that point the patient will be managed as described above. Further detail on how patients will be recruited and managed in this situation is provided in Section 9.

Adverse events (AEs) or hospital admissions related to camostat or COVID-19 will be followed up as per Section 12.0.

During the trial period (Days 1-28), patients who are hospitalised will also be followed up, up to 28 days post discharge.

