5.3.3 Dose interruptions/ Withdrawal criteria

- If a clinically significant abnormality is identified, camostat will be interrupted and blood samples will be taken for analysis.
- If abnormal results are identified, the patient will be referred to the GP for further assessment where local protocols will be followed.
- If required, patient hospital attendance with a suspected adverse event will trigger SAE reporting and the Investigator and Sponsor will make a causality assessment.
- Possible, Probably and Highly Probable causality assessment to camostat will result in treatment withdrawal.
- If the patient recovers symptomatically and biochemical analysis returns to the normal range, re-starting camostat can be considered by the Investigator and Sponsor to include an assessment whether the patient is likely to be past the initial stage of infection. For patients where it is deemed appropriate to re-start the patient, a maximum of 48 hrs treatment interruption will be allowable.

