Assessment ⁶	Testing site	Home (or at site if permitted)	Home visit	Daily video call (or phone)	Home visit (or at site if permitted)	Daily call	Home visit (or at site if permitted)	Video call (or phone)	Video call (or phone)
Blood (FBC& U&Es & other markers)							■		
Blood - PK		X							
Pregnancy test for women of childbearing potential									
Demographics		X							
▪ Height, weight									
▪ Medical history									
▪ Risk factors									
▪ COVID-19 symptoms check									
▪ COVID-age risk									
Delivery of camostat ^c				X					
Camostat administration ^E				X					
				X					
				(first dose)					
					X				
					(if patient recovered, discontinue camostat)				
Documentation of supplementary oxygen administration/ high-flow oxygen device						X			
Assessment of:		X				X		X	
▪ ordinal scale status assessment									
Call with clinical researcher				X		X		X	X

A. The intention is that home visits, by a clinical professional, occur on Days 7 and 14 to take research bloods, PK bloods and repeat swab. However, this requirement may change if patients are permitted to provide samples by visiting the site. If the Sponsor and site decide that sampling is not required, this will be communicated to the patient. The Day 7 and 14 video (phone) calls will still go ahead as planned regardless of sampling.

■

C. If randomised to the camostat arm, patients will also receive camostat tablets to last for 14 days.

D. Two readings a day.

E. Trial packs and, for those patients randomised to the treatment arm, camostat may be delivered by courier or site staff.

■

G. For community patients, home visits can be performed on site if permitted by government guidance. **For hospital based patients these assessments may be performed face to face, if feasible.**

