12.6 Specific Events of Interest

The following events will be closely monitored as trial specific events of interest:

- Shock or anaphylactoid symptoms such as decreased blood pressure, dyspnoea and pruritis
- Rash, pruritis
- Gastrointestinal events (nausea, abdominal discomfort, abdominal distension)
- Changes in liver enzymes (AST, ALT, GGT) or jaundice
- Thrombocytopenia
- Hyperkalaemia

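### The Day 7 and Day 14 sampling waiver does not say whether it covers the safety bloods, and the adverse event tables would count unsampled patients as free of laboratory events

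*Protocol*

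**What the plan says.** The waiver appears four times in the protocol: in the Synopsis (Section 2), Section 5.1, Section 8.3.2 and footnote A to Table 1. Section 8.3.2 reads "If the Sponsor and site decide that sampling is not required, this will be communicated to the patient". Only the calls are protected: "The Days 7 and 14 video (phone) calls will still go ahead as planned regardless of sampling". No criterion, substitute test or exemption is given.

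The same part of Section 8.3.2 lists, under "Biochemical and haematological investigations to include", a panel that includes platelets, potassium, ALT, AST, ALP and GGT. For raised values it refers the reader on: "For dose interruption/withdrawal criteria, see Section 5.3.3". Section 5.3.3 says "If a clinically significant abnormality is identified, camostat will be interrupted and blood samples will be taken for analysis", and restarting is considered once symptoms and biochemistry have recovered.

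Section 12.6 opens with "The following events will be closely monitored as trial specific events of interest". Three of its six items are wholly or mainly laboratory findings: liver-enzyme changes (or jaundice), thrombocytopenia and hyperkalaemia. Section 12.1.1 counts abnormal laboratory results as adverse events, and Section 13.1 makes the number and severity of adverse events the primary outcome.

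In the SAP document, Section 5.1 of the reporting analysis plan (RAP) defines the safety population by one dose taken, or by Day 1 completed in the control arm. Section 6.7 uses that population as the denominator for the adverse event tables.

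**The concern.** Safety is the primary objective, and three of the named events of interest depend mainly on a blood result. If a site reads the waiver as covering the safety panel, its community patients may have no planned blood test between screening and the end of follow-up. A laboratory abnormality without symptoms would not be found on a call. The patient would still sit in the denominator of every adverse event table as someone without the event. A zero in that table could then mean either not observed when measured or not measured, and the summary tables do not separate the two. The trial is meant to inform a Phase III decision, so this affects how much reassurance a low laboratory event count can give.

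**Working it through.** **Is the panel inside the waiver?** The four places read as follows.

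- Table 1, footnote A: the visits are "to take research bloods, PK bloods and repeat swab", then the waiver. This points to a narrow scope.
- Section 8.3.2 and the Synopsis: the sentence leading to the waiver names research bloods and a redacted item, which again points to a narrow scope. Both then list the haematology and biochemistry panel under the same visits without exempting it. The Synopsis lists the panel separately from the research samples.
- Section 5.1: the visits are described as being for blood draws and a swab, with no restriction to research samples, and the waiver follows. This points to a broad scope.

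Both readings are available, and no sentence chooses between them.

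**Are there other planned on-treatment safety bloods?** Section 8.1 has the panel at baseline. Section 8.3.1 (daily contact) and Section 8.3.3 (Days 21 and 28) show no readable blood test. RAP Tables 8 and 9 have columns for Screening, Day 7 and Day 14 only. Some bullets are redacted and the blood row of Table 1 is broken, so this rests on the readable text, which is consistent throughout. Waiving both draws therefore leaves no planned draw out of two. By the visit windows in Table 1, the draws fall on Days 6 to 8 and Days 12 to 14 of a 14-day course.

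**Who is in the denominator?** The safety population needs no post-baseline sample. The efficacy population, which Section 11.1 of the SAP appendix names for the primary analyses, needs none either.

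**Size.** The plan gives no precision for adverse event rates. Its only precision figure is for the recruitment rate: 50%, standard error 3.5%, interval 43% to 57%. It reproduces with 200 patients approached: √(0.5 × 0.5 / 200) = 3.54%, and 50% ± 1.96 × 3.54% = 43.1% to 56.9%. It has no bearing on this point.

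Inputs: up to 50 camostat patients (Synopsis). The number sampled, n, is an assumption because no waiver rate is stated. The n = 47 row corresponds to the general expectation of about 5% missing data in SAP appendix Section 11.2 (0.95 × 50 = 47.5). For the true event rate p, 1% is the edge of the under-1% incidences quoted in Section 3.3.1 for the licensed uses, and 5% is illustrative.

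- Exact two-sided 95% upper limit after zero events: 1 − 0.025^(1/n)
- Chance of at least one event among those sampled: 1 − (1 − p)^n

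| Sampled n | Upper limit after 0 events | Chance of ≥1 event, p = 1% | Chance of ≥1 event, p = 5% |
|---|---|---|---|
| 50 | 7.1% | 39.5% | 92.3% |
| 47 | 7.5% | 37.6% | 91.0% |
| 25 | 13.7% | 22.2% | 72.3% |
| 10 | 30.8% | 9.6% | 40.1% |
| 0 | no bound | 0% | 0% |

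In every row the adverse event table would show 0/50 if nothing was seen. As one-sided 95% bounds, the limits for n = 50 and n = 25 are 5.8% and 11.3%.

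**The case against.** The strongest reply is that the waiver was only ever meant for research bloods, PK bloods and swabs. The wording before it in three of the four places supports that, and the Synopsis treats the safety panel as a separate item. This is a reasonable reading, but it is not stated, and Section 5.1 does not carry it. If it is what was intended, one clarifying phrase settles the matter.

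A reader might infer that the waiver disables the interruption rule. The documents do not support that. The trigger in Section 5.3.3 is any clinically significant abnormality, not a laboratory value alone, and interruption itself calls for bloods, which can also supply the biochemistry considered at restart. Daily calls, clinical-care results (Section 8.1) and record review (Section 8.3.4) remain. Jaundice, rash, gastrointestinal and anaphylactoid events can be picked up without a planned draw.

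A reader might also infer that sampling will be waived patient by patient, or more often in one open-label arm, and so bias the comparison. The text does not rule this out, but nothing in it says so, and a joint decision by sponsor and site could equally be a site-level policy.

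Finally, missing results would not be hidden. RAP Section 6.8 lists laboratory results per patient, so blanks would show. That stands, but the summary adverse event tables would still carry the full denominator.

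**Conclusion.** The point holds as an unresolved scope with a reporting consequence. The waiver does not say whether it covers the safety panel. If it does, it is inconsistent with the close monitoring promised in Section 12.6. What could be lost is limited to symptomless laboratory abnormalities in community patients who have no for-cause or clinical-care bloods.

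The size depends wholly on how often safety bloods are waived, which the documents do not state and which could be anywhere from none to all. At the SAP appendix's general missing-data expectation the effect is trivial (upper limit 7.5% against 7.1%). With half of the camostat arm unsampled it is 13.7%, nearly double. With nobody sampled, a zero carries no information. The plan reports safety descriptively and gives no intervals for event rates, so these limits show how much a zero can exclude and are not figures that the plan misreports.

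The conclusion that Days 7 and 14 are the only planned on-treatment safety bloods rests on the readable schedule.

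**What to change.** - **Protocol.** Reconcile the waiver text in the Synopsis, Section 5.1, Section 8.3.2 and Table 1 footnote A with Sections 5.3.3 and 12.6. State whether the waiver covers the listed haematology and biochemistry. If it does not, say so in all four places. If it does, say how Sections 12.6 and 5.3.3 are then met, and that any waiver applies irrespective of arm. Which monitoring rule to adopt is for the sponsor and investigators.
- **Data capture.** Record each scheduled safety sample that was not taken, with the reason.
- **RAP.** Report the laboratory-defined events of interest by arm over patients with at least one scheduled post-baseline (Day 7 or Day 14) safety sample, next to the safety-population count, and show the number sampled in each arm. Report for-cause and clinical-care results separately: a denominator open to any on-study blood would admit patients tested because they were unwell and could inflate the rate.

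The cost is a wording change in four places, a little more data recording and one extra table. The sponsor and sites would have less discretion over waiving samples.
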